## Appendix C. Study Activities

		f Applicable							,	Year 1								
Procedure	WO Period	SCR Visit	Cycle 1 -3 ‡ PCV b	D 1°	M 1	M 2	M 3	M 4	M 5	M 6	M 7	M 8	M 9	M 10	M 11	M 12	Unsch Visit	PD (If Appl.)
Informed Consent	X	X&																
Phone Visit d					X	X		X	X		X	X		X	X			
Medical/Social History	X	X &		Xe														
Gynecological/ Obstetrical and Uterine Fibroid History	X	X &		X e														
Complete Physical Examination; Height (H); Weight (W)	X*	X (H, W) \$		X*,e												X (W) \$		X (W) \$
Gynecological (External Genitalia, Pelvic and Breast) Examination		X														X		X
Vital Signs	X	X	X	Xe			X			X			X			X	X	X
12-Lead Electrocardiogram (ECG)		X																
Mammogram		$X_{\infty}$														X f		X g
Pap Test		X																X g
Endometrial Biopsy h,i		X														X		X g
Pelvic Ultrasound @ : TAU, TVU	X j	X &		$X^k$												X		X g
Saline Infusion Sonohysterography (SIS) i		X																
MRI (if applicable) l		X																
DXA Scan		X								X						X		X g

[figure not shown]
		Applicab eening Per							,	Year 1								
Procedure	WO Period	SCR Visit	Cycle 1  -3 ‡ PCV b	D 1°	M 1	M 2	M 3	M 4	M 5	M 6	M 7	M 8	M 9	M 10	M 11	M 12	Unsch Visit	PD (If Appl.)
Dispense Sanitary Products and Collection Kit (Keg, Collection Bags, etc.)		X	Χ^															
Start Collection of Sanitary Products		X																
Return Sanitary Products; draw venous blood sample			X															
Clinical Safety Labs: Chemistry, Hematology, Lipid Panel and Urinalysis		X		X												X		X
Lipid Panel and Subset of Chemistry Labs: ALT, AST, Bilirubin and Alkaline Phosphatase							X			X			X					
Urine Test for Gonorrhea and Chlamydia (Optional)		X m																
Vitamin D Testing		X																
Serology (Hepatitis and HIV Screens)		X																
Endocrine: FSH and Reflexive TSH		X																
Biomarker Sample: Serum Estradiol (E2)				Xe			X n			X n			X n			X n		X n
Pharmacokinetic Sample (PK): Elagolix and NETA Plasma Concentration							X n			X n			X n			X n		X n

		Applicable							7	Year 1	Treat							
Procedure	WO Period	SCR Visit	Cycle 1 -3 ‡ PCV b	D 1°	M 1	M 2	M 3	M 4	M 5	M 6	M 7	M 8	M 9	M 10	M 11	M 12	Unsch Visit	PD (If Appl.)
Pharmacogenetic DNA and RNA Sample (PG) (Optional based on Subject consent)				X n												X n		X n
Urine Pregnancy Tests o,p	X	X	X	X	X	X	X	X	X	X	X	X	X	X	X	X		X
Contraception Counseling/Dispense Contraceptives as necessary q	X	X	X	X^	X	X	Χ^	X	X	X^	X	X	X^	X	X	X^		X
Birth Control Attestation				X			X			X			X			X		X
Reason for Study Participation				Xe														
PSQ				Xe														
UFS-QoL				Xe						X						X		X
PGIC-MB							X			X			X			X		X
C-SSRS – Baseline/ Screening		X		Xe														
C-SSRS – Since Last Visit							X			X			X			X		X
Randomization				X														
Interactive Response Technology (IRT)	X	X	X #	X			X			X			X			X		X
Dispense Study Drug				X			X			X			X			Xr		
Drug Accountability d					X	X	X	X	X	X	X	X	X	X	X	X		X
Adverse Event Monitoring d	X	X	X	X	X	X	X	X	X	X	X	X	X	X	X	X	X	X
Concomitant Medication Review d	X	X	X	X	X	X	X	X	X	X	X	X	X	X	X	X	X	X

D = Day; M = Month; SCR Visit = Screening Visit; WO = Washout; PCV = Product Collection Visit; Unsch Visit = Unscheduled Visit; PD = Premature Discontinuation Visit

- ‡ If the subject does not demonstrate blood loss > 80 mL during either Screening Cycle 1 or 2, she may qualify for a third cycle assessment of blood loss (Table 5). If required, the subject will collect sanitary products for a third menstrual cycle and will visit the site for a Screening Cycle 3 Product Collection Visit.
- & If performed during Washout, do not repeat during Screening Period.
- \* Brief symptom-directed examination.
- \$ Complete physical examination; including weight (the subject should not wear shoes during weighing).
- Only in subjects ≥ 39 years of age at the time of randomization, unless the mammogram was performed within 3 months prior to Screening. Results must be entered in EDC upon receipt.
- @ Subjects with a finding of polyp on pelvic ultrasound during the Treatment Period will undergo evaluation per standard of care which may include an SIS.
- ^ Site should dispense enough sanitary product collection kits during screening only. In addition, sites should also dispense contraceptives to carry subject over to the next on-site visit.

- 1. Subjects who have SIS images which were unable to fully assess the endometrial cavity after 2 separate SIS attempts have been made may undergo an MRI for further evaluation in Screening (per imaging vendor request only).
- m. Optional urine test for gonorrhea or chlamydia should be performed prior to undergoing the endometrial biopsy. Positive test results will be treated outside of the protocol.
- n. Biomarker sample (E2), Pharmacokinetic (PK) (elagolix and NETA) and Pharmacogenetic (DNA and RNA) samples can be drawn at any time during the visit.
- o. Study drug must not be dispensed if the subject has a positive urine pregnancy test result at any visit during the Treatment Period. A positive urine pregnancy test result must be confirmed with a quantitative serum pregnancy test. For any subject who has a positive serum pregnancy test result, a TVU must be conducted as early as possible in the first trimester in order to assess the gestational age and estimated due date. The site will immediately inform the subject to discontinue study drug and the subject will be discontinued from the study at the point the pregnancy is confirmed.
- p. Dispense home urine pregnancy test kits for subjects to self-administer during the Screening Period, prior to SIS and endometrial biopsy procedure, and for the Phone Visits during the Treatment Period.
- q. Subjects are required to use two forms of non-hormonal birth control throughout the Treatment Period. In addition, if the subject prematurely discontinues, the site should counsel the subject on the continued use of non-hormonal contraceptive use for at least 30 days after the last dose of study drug.
- r. Study drug kits will continue to be dispensed for those subjects continuing into the open-label Treatment Period.

[figure not shown]
# Study Activities – Year 2 Open Label Treatment Period

					Ye	ar 2 Treat	ment Per	iod a						
	M 13	M 14	M 15	M 16	M 17	M 18	M 19	M 20	M 21	M 22	M 23	M 24	Unsch Visit	PD
Phone Visit b	X	X		X	X		X	X		X	X			
Pelvic Ultrasound @ : TVU, TAU												X		X c
Endometrial Biopsy d												X		X c
Pap Test												X		X c
Complete Physical Examination: including weight (W)												X (W)*		X (W)*
Gynecological (External Genitalia, Pelvic and Breast) Examination												X		Х
Vital Signs			X			X			X			X	X	X
Mammogram e												X		X c
DXA Scan						X						X		X c
Clinical Safety Labs: Chemistry, Hematology, Lipid Panel and Urinalysis												X		X
Lipid Panel and Subset of Chemistry Labs: ALT, AST, Bilirubin and Alkaline Phosphatase			X			X			X					

					Yea	ar 2 Treat	ment Peri	iod a						
	M 13	M 14	M 15	M 16	M 17	M 18	M 19	M 20	M 21	M 22	M 23	M 24	Unsch Visit	PD
Biomarker Sample: Serum Estradiol (E2) f						X						X		X
Pharmacokinetic Sample (PK): Elagolix and NETA Plasma Concentration f						X						X		X
Urine Pregnancy Test g,h	X	X	X	X	X	X	X	X	X	X	X	X		X
Contraception Counseling/Dispense Contraceptives as necessary	X	X	X j	X	X	X j	X	X	X j	X	X	X j		Х
Birth Control Attestation			X			X			X			X		X
UFS-QoL						X						X		X
C-SSRS – Since Last Visit			X			X			X			X		X
Interactive Response Technology (IRT)			X			X			X			X		X
Dispense Study Drug			X			X			X			X		
Drug Accountability b	X	X	X	X	X	X	X	X	X	X	X	X		X
Adverse Event Monitoring b	X	X	X	X	X	X	X	X	X	X	X	X	X	X
Concomitant Medication Review b	X	X	X	X	X	X	X	X	X	X	X	X	X	X

- @ Subjects with a finding of polyp on pelvic ultrasound during the Treatment Period will undergo evaluation per standard of care which may include an SIS.
- \* Complete physical examination; including weight (the subject should not wear shoes during weighing).
- a. Refer to Table 1 Visit and Assessment Windows, for allowable visit and assessment-specific windows during the Year 2 Treatment Period.
- b. Site staff to evaluate subjects compliance with taking study drug per protocol, assess ongoing adverse events, concomitant medications (if applicable), obtain the results of the subject's self-administered urine pregnancy test, and remind subjects of the importance of consistent use of appropriate and effective use of dual non-hormonal contraception.

- c. Premature Discontinuation prior to the time of the Treatment Month 18 does not require a Mammogram, DXA, Pelvic Ultrasound, Pap test, or Endometrial Biopsy, (i.e., received < 6 months of study drug during the Year 2 Treatment Period). Refer to Section 5.3.1.1, Study Procedures, Bone Mineral Density (DXA scan) for additional details on performing DXA scan at Premature Discontinuation Visit.
- d. A negative urine pregnancy result should be obtained on the day of the endometrial biopsy, prior to performing the procedure. An endometrial biopsy is not required during the Treatment Period if the TVU findings indicate an endometrial thickness ≤ 4 mm. If the TVU findings indicate an endometrial thickness ≥ 4 mm then the subject must have an endometrial biopsy performed.
- e. Mammograms will be performed for all subjects who are 39 years of age or older at time of the scheduled study visit.
- f. Biomarker sample (E2), Pharmacokinetic (PK) (elagolix and NETA) samples can be drawn at any time during the visit.
- g. Study drug must not be dispensed if the subject has a positive urine pregnancy test result at a visit during the Treatment Period. A positive urine pregnancy test result must be confirmed with a quantitative serum pregnancy test. For any subject who has a positive serum pregnancy test result, a TVU must be performed during the first trimester of pregnancy to assess the gestational age and estimated date of delivery. The site will immediately inform the subject to discontinue study drug and the subject will be discontinued from the study at the point the pregnancy is confirmed.
- h. Home pregnancy test kits will be dispensed at on-site visits and will be self-administered at home by the subject and results will be reported to site.
- i. Subjects are required to continue the use of two forms of non-hormonal birth control throughout the Treatment Period. In addition, if the subject prematurely discontinues, the site should counsel the subject on the continued use of non-hormonal contraceptive use for at least 30 days after the last dose of study drug.
- j. Site should dispense enough contraceptives to carry subject over to the next on-site visit.

[figure not shown]

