## 5.3.1.1 Study Procedures

[figure not shown]
The study procedures outlined in Appendix C are discussed in detail in this section, with the exception of monitoring study drug accountability (Section 5.5.7), contraception counseling/contraceptive dispensing (Section 5.2.4), the collection of concomitant medication (Section 5.2.3) and adverse event information (Section 6.0). All study data will be recorded on the eCRFs with the exception of the select ePRO data and data from the central lab/imaging vendor.

The Screening Period will occur within approximately 2.5 to 5 months prior to administration of the first dose of study drug on Day 1 (Randomization). For procedures performed during the Screening Period and subsequently repeated (as allowed per protocol or at the discretion of the AbbVie TA SD), the procedure performed closest to dosing will serve as a baseline for clinical assessment.

Study procedures during the Treatment and Post-Treatment Follow-Up Periods should be performed within the visit windows specified in Table 1. Scheduled monthly visits during the Treatment and Post-Treatment Follow-Up Periods are based on a 28-day month.

This protocol provides recommendations regarding the sequence of procedures to be performed during the study. In no case should these recommendations outweigh clinical judgment or standard of care. If the protocol indicates that the AbbVie TA SD or MD is to be contacted prior to performing a procedure, yet the timing of the request would either interrupt a procedure or would interfere with standard of care and clinical judgment, then clinical judgment should prevail and the AbbVie TA MD should be notified afterwards.

Due to the long Screening Period, eligibility should be assessed throughout the Screening Period, including just prior to randomization to ensure that the subject continues to meet eligibility and that the results from all screening procedures are available prior to randomization.

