Subjects with a BMD decrease of > 8% in the lumbar spine, total hip, or femoral neck (any of the three regions) on any DXA scan performed during the Treatment Period (i.e., Months 6, 12, 18, 24, 30, 36, and 42) must be discontinued from study drug dosing and will enter the Post-Treatment Follow-Up Period.

DXA scans are also required if a subject premature discontinues for the following reasons:

- Subjects who discontinue prior to the Treatment Month 6 visit only if the reason for premature discontinuation is due to the occurrence of a fracture or any newly diagnosed bone condition
- Subjects who discontinue any time at the time of or after the Treatment Month 6 visit unless a DXA scan has been performed within 3 months of Premature Discontinuation.

However, if a subject is being discontinued from the study due to a T-score of < -2.5 in any region (the lumber spine, total hip or femoral neck), BMD decrease from baseline of > 8% in any region, or TA MD assessment, additional DXA scans do not need to be performed as a part of the Premature Discontinuation visit procedures. In these circumstances, the subject would enter into the Post-Treatment Follow-Up Period and continue with required BMD evaluations.

DXA scans of the lumbar spine, total hip, and femoral neck will be obtained at Post-Treatment Follow-Up Period at Months 6 and/or 12, except for subjects who prematurely discontinued less than 3 months during the Treatment Period.

If the BMD percent change from baseline of any post-baseline DXA cannot be provided by the central reader (i.e., due to scanner changes), then the TA MD must be consulted to confirm if the subject can continue study drug dosing. A BMD decrease at any anatomic location (lumber spine, total hip **or** femoral neck) that results in discontinuation from the study should be reported as an adverse event (Section 6.1.1).

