## 5.4.1 Discontinuation of Individual Subjects

In the event that a subject withdraws or is prematurely discontinued from study drug treatment, the subject should complete the Premature Discontinuation Visit as soon as possible (preferably within 2-7 days of last dose of study drug, if possible) and undergo

study procedures as outlined in Appendix C. Subjects who prematurely discontinue during the Treatment Period are expected to enter the Post Treatment Follow-Up Period for up to 12 months unless discontinuation is due to pregnancy.

These procedures should not interfere with the initiation of any new treatments or therapeutic modalities the Investigator determines are necessary to treat the subject's condition. The reason(s) for the discontinuation from the Treatment Period will be recorded in source and in the eCRFs.

If a subject becomes pregnant during the Treatment Period or within 30 days of the last dose of study drug, no additional study procedures, except an ultrasound will be conducted. Refer to Section 6.1.6 for instructions on reporting of a pregnancy to the Sponsor and the required follow-up on the subject/fetus and live births.

Subjects who prematurely discontinue will have a DXA scan performed at the Premature Discontinuation Visit:

- Subjects who discontinue prior to the Treatment Month 6 visit only if the reason for premature discontinuation is due to the occurrence of a fracture or any newly diagnosed bone condition.
- Subjects who discontinue any time at the time of or after the Treatment Month 6 visit, unless a DXA scan has been performed within the prior 3 months of Premature Discontinuation.

Subjects who prematurely discontinue from treatment and enter Post-Treatment Follow Up Period and have had a TAU/TVU and DXA within the prior 3 months will not be required to repeat these procedures at the Premature Discontinuation Visit.

If a subject is discontinued from the study with an ongoing adverse event or an unresolved laboratory result that is clinically significant (as determined by the Investigator), the Investigator will attempt to provide follow-up until a satisfactory clinical resolution of the laboratory result or adverse event is achieved.

Upon discontinuation from the Treatment Period, all used, unused and unopened study drug containers will be returned to the study site.

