## 6.1.6 Pregnancy

Pregnancy in a study subject must be reported to AbbVie within 1 working day of the site becoming aware of the pregnancy. Subjects who become pregnant during the Treatment or Post-Treatment Follow-Up Periods of the study must be discontinued (Section 5.4 and Section 5.4.1). A positive urine pregnancy test result must be confirmed with a serum pregnancy test. While waiting for the results of the serum pregnancy test, study drug should be temporarily discontinued pending results of the serum pregnancy test. If a serum pregnancy test result is positive at any time during the Treatment Period of the study, the site will immediately inform the subject to discontinue study drug. However, an ultrasound examination will be performed as early as possible during the first trimester of pregnancy to assess the gestational age and document an intrauterine pregnancy. Information regarding a pregnancy occurrence in a study subject and the outcome of the

pregnancy will be collected for any study subject with a positive serum pregnancy test after receiving at least one dose of study drug through 30 days following the last dose of study drug. The site will report a positive pregnancy test to the Sponsor, will follow the course of the subject's pregnancy, and report to the Sponsor on the health of the subject and fetus at each trimester, the newborn at the first post-delivery pediatrician visit and the infant 6-12 months post-delivery.

If the subject has a positive serum pregnancy test during the Treatment or Post-Treatment Follow-Up Periods of the study, no additional study procedures, including protocol required DXA scans, will be conducted. The following information on the outcome of the pregnancy should be collected: fetal outcome (e.g., spontaneous or elective abortion, live infant or still birth), date and mode of delivery, birth weight, birth length, gender, any congenital anomaly and medically significant complications during pregnancy or labor or delivery. For live infant births, information on the health of the infant will be collected from the first post-delivery pediatrician visit and at 6 to 12 months after delivery.

For each subject with a confirmed pregnancy, the Investigator will provide information about the option to participate in an elagolix pregnancy registry (P18-954) for pregnancy outcomes. The contact information for the Bloom Pregnancy Registry is in the Oriahnn/Orilissa label (pregnancy registry [contact]).

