- b. Site staff to evaluate subjects compliance with taking study drug per protocol, assess ongoing adverse events, concomitant medications (if applicable), obtain the results of the subject's self-administered urine pregnancy test, and remind subjects of the importance of consistent use of appropriate and effective use of dual non-hormonal contraception.

- c. Premature Discontinuation prior to the time of the Treatment Month 30 does not require a Mammogram, DXA, Pelvic Ultrasound, or Pap test (i.e., received < 6 months of study drug during the Year 3 Treatment Period). Endometrial Biopsy is not required if the subject had an endometrial biopsy within the last 6 months. Refer to Section 5.3.1.1, Study Procedures, Endometrial Biopsy, and Bone Mineral Density (DXA scan) for additional details on performing DXA scan at Premature Discontinuation Visit.
- d. A negative urine pregnancy result should be obtained on the day of the endometrial biopsy, prior to performing the procedure. Endometrial Biopsy is not required if the subject had an endometrial biopsy within the last 6 months. Refer to Section 5.3.1.1, Study Procedures, Endometrial Biopsy for additional details.
- e. A Mammogram will be performed for all subjects who are 39 years of age or older at time of the scheduled study visit.
- f. Biomarker sample (E2), Pharmacokinetic (PK) (elagolix and NETA) samples can be drawn at any time during the visit.
- g. Study drug must not be dispensed if the subject has a positive urine pregnancy test result at a visit during the Treatment Period. A positive urine pregnancy test result must be confirmed with a quantitative serum pregnancy test. For any subject who has a positive serum pregnancy test result, a TVU must be performed during the first trimester of pregnancy to assess the gestational age and estimated date of delivery. The site will immediately inform the subject to discontinue study drug and the subject will be discontinued from the study at the point the pregnancy is confirmed.
- h. Home pregnancy test kits will be dispensed at on-site visits and will be self-administered at home by the subject and results will be reported to site.
- i. Subjects are required to continue the use of two forms of non-hormonal birth control throughout the Treatment Period. In addition, if the subject prematurely discontinues, the site should counsel the subject on the continued use of non-hormonal contraceptive use for at least 30 days after the last dose of study drug.

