- b. Site staff to evaluate subjects compliance with taking study drug per protocol, assess ongoing adverse events, concomitant medications (if applicable), obtain the results of the subject's self-administered urine pregnancy test, and remind subjects of the importance of consistent use of appropriate and effective use of dual non-hormonal contraception.

- c. Premature Discontinuation prior to the time of the Treatment Month 42 does not require a Mammogram, DXA, Pelvic Ultrasound, or Pap test (i.e., received < 6 months of study drug during the Year 4 Treatment Period). Endometrial Biopsy is not required if the subject had an endometrial biopsy within the last 6 months. Refer to Section 5.3.1.1, Study Procedures, Endometrial Biopsy, and Bone Mineral Density (DXA scan) for additional details on performing DXA scan at Premature Discontinuation Visit.
- d. A negative urine pregnancy result should be obtained on the day of the endometrial biopsy, prior to performing the procedure. Endometrial Biopsy is not required if the subject had an endometrial biopsy within the last 6 months. Refer to Section 5.3.1.1, Study Procedures.
- e. A Mammogram will be performed for all subjects who are 39 years of age or older at time of the scheduled study visit.
- f. Biomarker sample (E2), Pharmacokinetic (PK) (elagolix and NETA) samples can be drawn at any time during the visit.
- g. Study drug must not be dispensed if the subject has a positive urine pregnancy test result at a visit during the Treatment Period. A positive urine pregnancy test result must be confirmed with a quantitative serum pregnancy test. For any subject who has a positive serum pregnancy test result, a TVU must be performed during the first trimester of pregnancy to assess the gestational age and estimated date of delivery. The site will immediately inform the subject to discontinue study drug and the subject will be discontinued from the study at the point the pregnancy is confirmed.
- h. Home pregnancy test kits will be dispensed at on-site visits and will be self-administered at home by the subject and results will be reported to site.
- i. Subjects are required to continue the use of two forms of non-hormonal birth control throughout the Treatment Period. In addition, if the subject prematurely discontinues, the site should counsel the subject on the continued use of non-hormonal contraceptive use for at least 30 days after the last dose of study drug.

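### Appendix C waives the exit DXA in nominal Months 15–18, 27–30 and 39–42, where Sections 5.3.1.1 and 5.4.1 require it

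*Protocol*

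**What the plan says.** Footnote c of the Appendix C activity tables governs the Premature Discontinuation Visit in each open-label year:

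- Year 2: "Premature Discontinuation prior to the time of the Treatment Month 18 does not require a Mammogram, DXA, Pelvic Ultrasound, Pap test, or Endometrial Biopsy".
- Year 3: "Premature Discontinuation prior to the time of the Treatment Month 30 does not require a Mammogram, DXA, Pelvic Ultrasound, or Pap test".
- Year 4: "Premature Discontinuation prior to the time of the Treatment Month 42 does not require a Mammogram, DXA, Pelvic Ultrasound, or Pap test".

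None of the three makes the DXA waiver depend on how long ago the last scan was. Each then refers the reader to Section 5.3.1.1 for further detail on the exit DXA.

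The body text has a different rule. Section 5.3.1.1, Bone Mineral Density, lists those who need an exit scan, including "Subjects who discontinue any time at the time of or after the Treatment Month 6 visit unless a DXA scan has been performed" in the preceding 3 months. Section 5.4.1 repeats it: "Subjects who discontinue any time at the time of or after the Treatment Month 6 visit, unless a DXA scan has been performed" in the preceding 3 months. Neither section restarts the count each year.

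The two places also point at each other. Section 5.4.1 tells sites to carry out "study procedures as outlined in Appendix C" at the exit visit, and Section 5.3.1.1 opens by stating: "The study procedures outlined in Appendix C are discussed in detail in this section". No sentence says which one prevails.

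**The concern.** Characterizing BMD over up to 48 months is the second of the two study objectives. SAP 9.5.2.2 measures bone recovery after treatment as the share of the loss at the final treatment scan that has been regained at follow-up. That final scan is the denominator. If it is several months old at exit, loss in the last months on drug is missed and recovery is misstated.

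Recovery is summarized in seven exit-time strata, and only some of them contain a period in which the footnote and the body text disagree. Scan age would then differ between strata because of a footnote, not because of anything about the women in them.

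Women who switched from placebo at Month 12 are a special case. One who stops in Months 15–18 without an exit scan may have no DXA on elagolix at all.

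The footnotes also carry no exception for fracture. Even before Month 6, the body rule asks for a scan when the stop is due to a fracture or a new bone condition. Read literally, footnote c waives it for a woman who stops at Month 16 for that reason.

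**Working it through.** **Inputs.** Scheduled on-treatment scans at Months 6, 12, 18, 24, 30, 36, 42 and 48 (Section 5.3.1.1). One month is 28 days (Definition of Terms). DXA window −15 or +4 days (Table 1). COVID-19 delay of up to 1 month (Section 5.3.1.1). Recovery formula, its example and the strata (SAP 9.5.2.2). Phase 2b Cohort 1 mean lumbar-spine change on this regimen, −0.1% at Month 6 (Section 3.2.2).

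**Where the rules disagree (Year 2).** The Month 12 scan falls on day 12 × 28 = 336. The body rule stops excusing the exit scan after 336 + 84 = 420. The footnote excuses it until Month 18, day 18 × 28 = 504. The rules conflict on days 421–503, which is 83 of the 504 − 336 = 168 days, or 49%. The same steps give days 757–839 in Year 3 and 1093–1175 in Year 4. In nominal months these are 15–18, 27–30 and 39–42.

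| Year 2 scan timing | 3 months = 84 days | 3 months = 91 days |
|---|---|---|
| 15 days early | 98 days, from Month 14.5 | 91 days, from Month 14.7 |
| on schedule | 83 days, from Month 15.0 | 76 days, from Month 15.3 |
| 4 days late | 79 days, from Month 15.1 | 72 days, from Month 15.4 |
| 4 days late plus 28-day COVID delay | 51 days, from Month 16.1 | 44 days, from Month 16.4 |

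The conflict never disappears. There is none in the first 3 months after an annual scan, when both rules excuse the DXA, or from Month 18, 30 or 42 to the end of that year, when footnote c no longer excuses it.

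**Age of the last scan at exit.** Let t be months since the scheduled scan, assumed uniform on 0–6.

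- Footnote: age = t, so the mean is 3.0 and the maximum 6.
- Body rule: age = t for t ≤ 3 and about 0 after that. The mean is (½ × 3²)/6 = 0.75 and the maximum 3.
- Inside the conflict window (t from 3 to 6): mean 4.5 under the footnote, about 0 under the body rule.

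**Strata.** The seven are Months 6–12, 12–18, 18–24, 24–30, 30–36, 36–42, and after 42 or completed. Three (12–18, 24–30, 36–42) contain a conflict window and four do not.

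**Effect on recovery.** Recovery = 100 × (final − follow-up)/final. The SAP example has final −2% and follow-up −1%: 100 × (−2 + 1)/(−2) = 50%, which reproduces its figure. At a loss of 0.1% per 6 months:

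- 3-month-old scan: final reads −1.95, so 100 × (−0.95)/(−1.95) = 48.7%.
- 6-month-old scan: final reads −1.90, so 100 × (−0.90)/(−1.90) = 47.4%.

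Individuals can differ more. In Cohort 1 on this regimen, 6.3% + 2% = 8.3% had a lumbar-spine decrease of 3% or more at Month 6, a figure that includes measurement error.

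**Placebo switcher stopping in Months 15–18 without an exit scan.** Her last DXA is the Month 12 scan. If it was done on or before the day elagolix started, it is also her baseline under the elagolix-initiation definition in SAP 9.1. Her change is 0%. SAP 9.5.2.2 defines recovery only after a decrease, so hers is undefined.

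**The case against.** The strongest reply is that the protocol largely settles the matter itself. Of the procedures waived in the Year 2 footnote, only DXA comes with a referral to Section 5.3.1.1, and that section and Section 5.4.1 agree. Year 1 footnote g has the same form: a general waiver before Month 6, then a referral to the section that adds the fracture scan back. A careful site would reach the stricter rule. This reduces the ambiguity but does not remove it. The referral promises only further detail, the waiver names DXA outright, and no order of precedence is given.

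Second, SAP 9.5.2.2 repeats the percent-change analysis for women who have a scheduled scan and a follow-up scan and stop before the next scheduled assessment. This is the affected group, and that analysis needs no exit scan. SAP 9.5.2.1 also cross-tabulates scans performed against treatment completion. Both help. Neither changes the recovery denominator, and the cross-tabulation does not isolate the three windows.

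Third, the harm is limited, and this stands. Recovery is descriptive, follow-up DXAs are unaffected, and the 3.0 against 0.75 month contrast supposes that every site follows the footnote. Women stopped for a T-score below −2.5, a loss above 8% or a medical director's assessment need no exit scan under the body rule either. The 8.3% describes the first 6 months of treatment, not later half-years, so it is only illustrative.

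Fourth, SAP 9.1 names no baseline for the Follow-Up Period, so the switcher result depends on carrying over the elagolix-initiation baseline; she might simply be counted as missing. Either way she has no BMD measured on elagolix. Switchers who stop in Months 12–15 lack one under both rules.

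**Conclusion.** The concern holds. Footnote c in Years 2, 3 and 4 excuses an exit DXA that Sections 5.3.1.1 and 5.4.1 require, for roughly half of each 6-month waiver window, and the overlap survives every scan-timing variation tried. Following the footnote doubles the maximum age of the last on-treatment scan in three of the seven recovery strata, from 3 to 6 months, and raises the mean from 0.75 to 3.0 months if stops are evenly spread.

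The expected distortion of average recovery is small: 1 to 3 percentage points in the SAP's example, assuming the Phase 2b mean loss continues at the same rate. The documents do not allow a count of scans lost. The point still deserves correction because sites act on these footnotes at the exit visit, the missing measurement cannot be recovered, and it bears on a stated objective.

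**What to change.** In footnote c of the Year 2, 3 and 4 tables, delete DXA from the list of waived procedures and add one sentence: *DXA is required unless performed within the prior 3 months, with the exceptions in Sections 5.3.1.1, 5.4.1 and 6.1.6 (T-score < −2.5, > 8% loss, TA MD assessment, pregnancy).* The pregnancy exception must stay, because Section 6.1.6 says that after a positive serum test "no additional study procedures, including protocol required DXA scans, will be conducted". The Year 3 and Year 4 footnotes already use a time-since-last-procedure condition for the endometrial biopsy, so the form is familiar to sites.

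Send sites a memo that Section 5.3.1.1 governs the exit DXA. For exits that have already happened, list the DXAs not done in the three windows and report the count with the recovery tables.

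The cost is one sentence in three footnotes, a memo and a listing. No procedure is added beyond those the body text already requires. The change does not help switchers who stop in Months 12–15.
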